10.3 POPULATIONS FOR ANALYSES

Intention to treat: any subjects who enroll onto the trial and provide consent and who receive at least 1 dose of SX-682, will be included in safety analyses in Arms 1 and 2.

In Arm 3, any participants who receive at least one cycle (defined as 28 days) of SX-682, M7824, and CV301 will be included in safety evaluations as well as efficacy evaluations for the appropriate cohort.

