3.1.5 Expansion Cohorts (Arm 3, Cohorts 2 and 3)

The safety, tolerability and efficacy evaluation of combination will continue with the RP2D of SX-682, M7824 and CV301 found during the dose escalation cohort (Arms 1 and 2). The dose of SX-682 used in combination with M7824 and CV301 in Arm 3 cannot exceed the highest tolerable dose for SX-682 monotherapy as determined in Arms 1 and 2.

Enrollment into the expansion cohorts can commence after the RP2D has been determined (after the 6th participant on relevant dose level completes the DLT evaluation period). For performance of the expansion cohorts, see **Schema 3**

Schema 3 Expansion Cohorts in Triple Negative Breast Cancer and HPV negative HNSCC

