3.4 DOSE MODIFICATIONS

3.4.1 General Rules

When, at the beginning of a treatment week, treatment delay related to one of study drugs is indicated, treatment with other drugs should not be delayed.

If, in the opinion of the investigator, a toxicity is considered to be due solely to one drug, the dose of other drugs does not require modification.

Any of the trial drugs may be held for toxicity per the discretion of the primary investigator if it is felt that the toxicity can be directly linked to a specific drug. For AEs that are attributed to a study drug, a study drug may be held or reduced (only SX-682 can be reduced) when in the opinion of the investigator doing so will minimize the risks to the participant and maximize clinic benefit (e.g., in the event of observed tumor reduction but also intolerable ADRs at the full dose).

If one drug is discontinued during first year of treatment, a participant may per PI discretion continue treatment with 2 other drugs. However, if 2 drugs must be discontinued, the participant will be taken off treatment. If one drug is discontinued during second year of treatment, a participant may per PI discretion continue treatment with the other drug.

For non-medical logistical reasons, unrelated acute illnesses, or palliative radiation, dosing with any drug can be delayed up to 2 months. Where at all possible, dosing should be restarted to keep in line with the original treatment schedule.

For AEs that are unrelated to the study drugs, study drug(s) may be held for up to 2 months at the discretion of the PI.

Any dose that would have occurred within this window will be skipped and the dose not made up.

If a participant on trial continues to gain benefit from treatment with one or more of the trial drugs at the two-year mark, the investigator can discuss with the CRADA partners the possibility of continuing the participant on treatment with the assigned trial drugs for an additional specified period of time.

In case of Grade 3 and Grade 4 AEs not study drug related, the study treatment may be interrupted based on the Investigator assessment and the subject will be medically treated for the event.

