6 DATA COLLECTION AND EVALUATION

6.1 DATA COLLECTION

The PI will be responsible for overseeing entry of data into a 21 CFR Part 11-compliant data capture system provided by the NCI CCR and ensuring data accuracy, consistency and timeliness. The principal investigator, associate investigators/research nurses and/or a contracted data manager will assist with the data management efforts. Primary and final analyzed data will have identifiers so that research data can be attributed to an individual human subject participant.

All adverse events, including clinically significant abnormal findings on laboratory evaluations, regardless of severity, will be followed until return to baseline or stabilization of event.

Document AEs from the administration of the first study intervention through 30 after the study agent (s) was/were last administered. Beyond 30 days after the last intervention, only adverse events which are serious and related to the study intervention need to be recorded.

An abnormal laboratory value will be recorded in the database as an AE only if the laboratory abnormality is characterized by any of the following:

- Results in discontinuation from the study

- Is associated with clinical signs or symptoms
- Requires treatment or any other therapeutic intervention
- Is associated with death or another serious adverse event, including hospitalization.
- Is judged by the Investigator to be of significant clinical impact

If any abnormal laboratory result is considered clinically significant, the investigator will provide details about the action taken with respect to the test drug and about the participant's outcome.

Adverse Events of grade 1 will not be collected.

End of study procedures: Data will be stored according to HHS, FDA regulations and NIH Intramural Records Retention Schedule as applicable.

Loss or destruction of data: Should we become aware that a major breech in our plan to protect subject confidentiality and trial data has occurred, his will be reported expeditiously per requirements in section [7.2.1](#)

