10.3.1 Evaluable for toxicity

All participants will be evaluable for toxicity from the time of their first treatment with SX-682. Participant will be eligible for the DLT evaluation if at least ≥ 85 percent of SX-682 scheduled doses were taken and 100% of scheduled doses of M7824 or CV301 were administered within the DLT period.

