10.4.5 Safety Analyses

The fraction of participants who experience a toxicity, by grade and type of toxicity, will be tabulated per dose level (both single agent and combination of agents) during the Arms 1 and 2 portion of the trial. Participants who take one dose or more of SX-682 will be evaluable for safety.

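### Section 10.3 admits Arm 3 participants to safety only via a full 28-day cycle of all three drugs, contradicting 10.3.1; the primary ORR has no named denominator and no all-treated ORR is planned

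*Combined protocol and SAP*

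**What the plan says.** **Safety.** Section 10.3 sets two entry rules. For the dose-escalation arms it takes subjects "who receive at least 1 dose of SX-682, will be included in safety analyses in Arms 1 and 2". For Arm 3, "any participants who receive at least one cycle (defined as 28 days) of SX-682, M7824, and CV301 will be included in safety evaluations", and the same sentence extends the criterion to efficacy. Section 10.3.1 has no arm limit: "All participants will be evaluable for toxicity from the time of their first treatment with SX-682". Section 10.4.5 ends "Participants who take one dose or more of SX-682 will be evaluable for safety", but the toxicity table it describes "will be tabulated per dose level (both single agent and combination of agents) during the Arms 1 and 2 portion of the trial". No Arm 3 toxicity table is specified, although section 3.1.5 states: "The safety, tolerability and efficacy evaluation of combination will continue with the RP2D of SX-682, M7824 and CV301".

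**Response.** Section 10.3 requires one cycle of all three drugs for Arm 3 efficacy. Section 10.3.2 requires measurable disease, one cycle of therapy and a re-evaluation, and also accepts objective progression before first restaging if a cycle was given. The two-stage rules in 10.2 and the interim look in 10.4.7 count evaluable participants. Section 10.4.2, the primary analysis, reports the fraction responding in each cohort with a 95% interval and does not say which population it uses. Section 10 plans no ORR among all treated Arm 3 participants.

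**The concern.** Two analysts following section 10 could produce different Arm 3 safety denominators. On the reading that gives the Arm 3 sentence in 10.3 any function for safety, the participants dropped are those with the earliest and most severe outcomes. That includes participants who lose one drug in cycle 1 but stay on treatment, since section 3.4.1 says: "If one drug is discontinued during first year of treatment, a participant may per PI discretion continue treatment with 2 other drugs".

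For ORR, a participant who loses one drug in cycle 1 and is later scanned is out under 10.3 and arguably in under 10.3.2. Under 10.3.2 two groups are left out altogether:

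- those lost before completing cycle 1;
- those with a cycle but no later scan and no objective progression.

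If these participants respond less often than those evaluated, the reported ORR exceeds the ORR among everyone treated, and the plan supplies no figure from which a reader could see the gap.

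**Working it through.** **1. Reproducing the plan's designs (section 10.2).** With first-stage size n1, futility bound r1, total n, final bound r and n2 = n − n1:

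P(go) = Σ over x > r1 of Bin(x; n1, p) × P(Bin(n2, p) > r − x)

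| Cohort | Rule | P(stop early) at p0 | P(go) at p0 | P(go) at p1 |
|---|---|---|---|---|
| TNBC (p0 0.05, p1 0.20) | stop at 0/12; go at 3 or more of 21 | 0.95^12 = 0.540 | 0.0804 | 0.8033 |
| HNSCC (p0 0.15, p1 0.40) | stop at 0–1/9; go at 5 or more of 16 | 0.85^9 + 9 × 0.15 × 0.85^8 = 0.599 | 0.0743 | 0.8149 |

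The stated early-termination probabilities (54.0% and 60.0%) and the stated alpha and beta limits are met. The sample sizes are not in question.

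**2. Safety denominator.** If both cohorts fill, 21 + 16 = 37 participants are evaluable. The documents give no early-loss rate, so suppose that 1, 2 or 3 further participants die, stop for toxicity or lose a drug in cycle 1. Intervals are Clopper-Pearson 95%.

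| Denominator | Events | Rate | 95% CI |
|---|---|---|---|
| One-cycle set (10.3) | 0/37 | 0% | 0–9.5% |
| All dosed, 1 lost | 1/38 | 2.6% | 0.1–13.8% |
| All dosed, 2 lost | 2/39 | 5.1% | 0.6–17.3% |
| All dosed, 3 lost | 3/40 | 7.5% | 1.6–20.4% |

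**3. ORR at the smallest passing count**, adding excluded participants as non-responders:

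- TNBC: 3/21 = 14.3% (3.0–36.3%) becomes 3/22 = 13.6% with one excluded and 3/23 = 13.0% (2.8–33.6%) with two.
- HNSCC: 5/16 = 31.3% (11.0–58.7%) becomes 5/17 = 29.4% with one and 5/18 = 27.8% (9.7–53.5%) with two, still above the 25% that section 10.2 calls desirable.

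**4. Effect on the decision rule.** Let e be the fraction excluded and f their response rate relative to those evaluated. If the all-treated ORR equals p0, the evaluable ORR is p0 / [(1 − e) + e·f]. For example, at e = 0.10 and f = 0 it is 0.05/0.90 = 0.0556 (TNBC) and 0.15/0.90 = 0.1667 (HNSCC). The plan's spare places are 105 − (60 + 21 + 16) = 8, shared by all arms; spread evenly, 8/105 = 7.6%. With f = 0:

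| e | P(go) TNBC | P(go) HNSCC |
|---|---|---|
| 0 | 0.080 | 0.074 |
| 7.6% | 0.097 | 0.098 |
| 10% | 0.103 | 0.107 |
| 20% | 0.133 | 0.157 |

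With one, two or three lost per filled cohort, e = m/(21 + m) for TNBC (4.5%, 8.7%, 12.5%) and m/(16 + m) for HNSCC (5.9%, 11.1%, 15.8%). P(go) is then 0.090, 0.099 and 0.109 for TNBC, and 0.092, 0.111 and 0.133 for HNSCC.

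P(go) passes 0.10 at about e = 9.0% (TNBC) and 8.2% (HNSCC). With f = 0.5 the divisor is 1 − 0.5e, so these points double to about 18% and 16%. With f = 1 there is no inflation.

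**The case against.** **The wording of 10.3 is inclusive.** It never says that only these participants count, so it could be read together with 10.3.1 and the last sentence of 10.4.5. That reading is available, but it leaves the separate Arm 3 criterion with nothing to do for safety, and the one Arm 3-specific statement is the one that excludes. The sentence needs correcting on either reading.

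**Safety oversight is intact.** This stands. Section 6.1 says "Document AEs from the administration of the first study intervention", and SAE reporting (8.2), the halting rule (3.2) and DSMB review (7.5.2) all see cycle 1 events. The defect is confined to the reported denominator. The 0/37 figure is also true by construction and needs both cohorts to reach full size; at p0 the chance of passing stage 1 is 46.0% for TNBC and 40.1% for HNSCC.

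**The ORR denominator can be inferred.** As the specific definition, 10.3.2 most plausibly governs the evaluable counts in 10.2 and 10.4.7. That is fair for the stage rules. It is still not tied to 10.4.2, and 10.3 states a different efficacy criterion for the same arm.

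**An all-treated ORR is a preference in a preliminary-efficacy study, and few should be missed.** Post-treatment assessment (3.5, footnote 13), extra scans (6.3) and the instruction to document progression (note to Table 12) do shrink the unscanned group. Off-treatment imaging is nevertheless optional (3.5, footnote 8), and none of these provisions recovers participants lost before completing cycle 1. The numerical effect is small at plausible loss: at 7.6%, P(go) stays under 0.10 even if every excluded participant is a non-responder.

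**Conclusion.** The concern holds and should be fixed before Arm 3 is analysed. The Arm 3 safety criterion in 10.3 is a wrong rule that conflicts with 10.3.1: followed as written, it reports as zero a class of early severe outcomes that would be 2.6% to 7.5% of those dosed with one to three losses. The primary ORR has two candidate populations, neither named in 10.4.2, and no all-treated figure.

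The consequence for the response decision is modest. It exceeds the stated alpha of 0.10 only above about 9.0% (TNBC) or 8.2% (HNSCC) loss, and only if the excluded are all non-responders and p0 is an all-treated rate, which the plan does not say. The loss rates are assumed ranges, because the documents give none. The two-stage designs themselves are sound.

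**What to change.** 1. **Safety set.** In 10.3, define the Arm 3 safety population as all participants who receive at least one dose of any study drug, which matches AE collection from first intervention in 6.1. Bring 10.3.1 and 10.4.5 into line, and extend the 10.4.5 toxicity tabulation to Arm 3 by cohort.
2. **ORR.** In 10.4.2, name the denominator by reference to 10.3.2. In 10.3.2, say whether a cycle in which one drug was stopped counts as a cycle, and make 10.3 agree. Add for each cohort an ORR with 95% interval in all treated participants with measurable disease, counting those without a post-baseline assessment as non-responders. Report the number excluded from the evaluable set and the reasons.
3. **Useful alongside.** State in 10.2 whether p0 and p1 are all-treated or evaluable rates, and whether inevaluable Arm 3 participants are replaced. The evaluable counts and the 105 ceiling imply replacement but do not state it.

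The cost is wording in section 10, one toxicity table and one extra proportion per cohort, all from data already collected. N, stage rules and procedures do not change. The all-treated ORR may come out slightly lower.

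Moving the Simon counts to all treated participants is optional. If p1 is an evaluable-only rate, the success probability per participant becomes p1(1 − e), and power falls from 80.3% (TNBC) and 81.5% (HNSCC) to 77.2% and 77.0% at 5% loss, 75.4% and 74.3% at 7.6%, and 73.7% and 71.8% at 10%. That is below the stated 80% and would have to be disclosed.

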3.4.4.1 Adverse Drug Reactions (ADRs) Requiring Treatment Discontinuation

All adverse events in this trial will be graded using the NCI Common Terminology Criteria for Adverse Events (CTCAE) version 5.0.

Any Grade 4 ADRs require permanent treatment discontinuation except for any of the following:

- Single laboratory values out of normal range that do not have any clinical correlate and resolve to Grade ≤ 1 or Baseline grade within 7 days with adequate medical management.
- Grade 4 symptomatic endocrinopathies (e.g., thyroiditis or hypophysitis), treatment should be delayed, and treatment started according to best medical judgement based on the most updated professional guidelines (NCCN, EMSO, SITC, etc.). Following the initiation of appropriate medical therapy for the endocrinopathy, treatment can be resumed per PI discretion.

- Asymptomatic lab abnormalities (Grade 3 or 4) as described below in the Grade 3 ADR section.
- Grade 4 non-tumor bleeding will not require permanent treatment discontinuation if an alternative explanation for the bleeding is identified. If no alternative explanation is identified, treatment must be permanently discontinued.

Any Grade 3 ADRs require treatment temporary discontinuation except for any of the following:

- Transient (\leq 48 hours) Grade 3 flu-like symptoms or fever, which is controlled with medical management.
- Transient (\leq 48 hours) Grade 3 fatigue, local reactions, headache, nausea, emesis that is controlled with medical management.
- Tumor flare phenomenon defined as local pain, irritation, or rash localized at sites of known or suspected tumor.
- Any single Grade \geq 3 drug-related transaminase, alkaline phosphatase, or bilirubin abnormality with no other associated laboratory (or other) abnormality that is not associated with symptoms or clinical manifestations of hepatitis. If the liver function abnormality not associated with symptoms or clinical manifestations of hepatitis has not resolved to Grade \leq 1 within the subsequent 2 cycles (56 days), the subject should permanently discontinue treatment with M7824.

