10.4.2 Analysis of the Primary Endpoints

The toxicity grades per participant will be tabulated and reported by dose level during dose escalation (Arms 1 and 2). This will also include separate evaluations for the initial monotherapy evaluations preceding the evaluation of the combination at each dose level.

In Arm 3, the fraction of participants who experience a response in each disease-specific cohort will be reported along with 95% two-sided confidence intervals.

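### The Arm 3 safety set is defined in conflicting ways, the arm-specific rule drops cycle-1 leavers, and section 10.4 plans no Arm 3 toxicity table

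*Combined protocol and SAP*

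**What the plan says.** Section 10.3 gives two safety rules in succession. In Arms 1 and 2, consented and enrolled participants count once they have had one dose of SX-682. For Arm 3 the rule changes: "any participants who receive at least one cycle (defined as 28 days) of SX-682, M7824, and CV301 will be included in safety evaluations", and the same participants form the efficacy set.

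Section 10.3.1, on evaluability for toxicity, reads: "All participants will be evaluable for toxicity from the time of their first treatment with SX-682". It names no arm. Section 10.4.5 ends with "Participants who take one dose or more of SX-682 will be evaluable for safety", again with no arm named, although the sentence before it concerns dose escalation.

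On output, 10.4.5 has toxicity by grade and type "tabulated per dose level (both single agent and combination of agents) during the Arms 1 and 2 portion of the trial". Section 10.4.2 also limits its toxicity table to dose escalation. For Arm 3, section 10.4 lists response, disease control, PFS, the stage-one response count, separate analysis by histology and exploratory work. Yet 3.1.5 says of the expansion cohorts: "The safety, tolerability and efficacy evaluation of combination will continue with the RP2D of SX-682, M7824 and CV301".

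**The concern.** A safety population that requires a completed treatment period is selected on the outcome it is meant to describe. Participants who cannot tolerate the first 28 days, or who die in them, are not counted. Cycle 1 is also when Arm 3 does something new: the study calendar (3.5, footnote 3 and Table 8) gives Arm 3 no SX-682 lead-in, so its participants start all three drugs together, whereas Arm 2 participants have already had two weeks of SX-682.

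At stake is the reported tolerability of the triplet at the RP2D. An analyst must choose between two denominators, and the only rule that names Arm 3 is the one open to this bias. If 10.4 is followed literally, there is no Arm 3 toxicity table at all.

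**Working it through.** The plan states no figure on this point, so the check sets the text side by side and then uses simple proportions.

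**1. Which rule applies to Arm 3?**

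| Section | Arm named | Entry to the safety or toxicity set |
|---|---|---|
| 10.3, first rule | 1 and 2 | One dose of SX-682 |
| 10.3, second rule | 3 | One 28-day cycle of all three drugs |
| 10.3.1 | None (all participants) | First SX-682 treatment |
| 10.4.5, last sentence | None | One dose of SX-682 |

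The firm conflict is the second rule of 10.3 against 10.3.1. The 10.4.5 sentence is weaker evidence because it follows text about Arms 1 and 2; the conflict does not need it.

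**2. Can toxicity remove someone from the one-cycle set?** Yes. For M7824, 3.4.4.1 says: "Any Grade 4 ADRs require permanent treatment discontinuation except for any of the following". It also requires permanent discontinuation for grade 3 non-tumor bleeding needing intervention or hospitalization, unless another explanation is found. M7824 is due on Days 1 and 15. A participant stopped between those days has had one of the two doses in the cycle. Section 3.4.1 allows the rest of treatment to go on: "If one drug is discontinued during first year of treatment, a participant may per PI discretion continue treatment with 2 other drugs". That participant still has not had a full cycle of M7824. Someone who stops all drugs or dies before Day 28 is outside the set on any reading.

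**3. Size, on assumed counts.** Inputs from 10.2:

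- Arm 3 evaluable maximum: 21 + 16 = 37.
- Evaluable maximum over all arms: 60 + 21 + 16 = 97.
- Accrual ceiling 105, so 105 − 97 = 8 spare places, shared by all arms.

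Assume that 37 participants complete a cycle, *a* of them with grade 3 or worse toxicity, and that *n* more leave in cycle 1, *k* of them with such toxicity.

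- One-cycle set: *a*/37
- All treated: (*a* + *k*)/(37 + *n*)
- The one-cycle set understates the rate when *k*/*n* > *a*/37.

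With *a* = 6 the one-cycle rate is 6/37 = 16.2%, and break-even is *k*/*n* = 6/37, about one leaver in six. All-treated rates:

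| *n* | *k* = 0 | *k* = 1 | *k* = 2 | *k* = 4 |
|---|---|---|---|---|
| 2 | 6/39 = 15.4% | 7/39 = 17.9% | 8/39 = 20.5% | – |
| 4 | 6/41 = 14.6% | 7/41 = 17.1% | 8/41 = 19.5% | 10/41 = 24.4% |
| 8 | – | 7/45 = 15.6% | 8/45 = 17.8% | – |

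The row *n* = 8 uses every spare place in the trial. Dashes mark combinations that are impossible or were not calculated.

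Sensitivity to the assumed base, at *n* = *k* = 2:

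- *a* = 4: 6/39 − 4/37 = 15.4% − 10.8% = 4.6 points
- *a* = 6: 8/39 − 6/37 = 20.5% − 16.2% = 4.3 points
- *a* = 10: 12/39 − 10/37 = 30.8% − 27.0% = 3.7 points (from unrounded values)

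**4. A toxicity seen only in early leavers.** The one-cycle set reports 0/37 however many there are. In all treated, one case is 1/38 = 2.6%, two are 2/39 = 5.1% and four are 4/41 = 9.8%. By cohort, two cases are 2/23 = 8.7% (TNBC, 21 completers) or 2/18 = 11.1% (HNSCC, 16 completers).

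**5. How many might leave?** If a fraction *q* of treated participants fails to complete a cycle, the number left out is 37/(1 − *q*) − 37. For assumed *q* of 2%, 5%, 10% and 15% this is 0.8, 1.9, 4.1 and 6.5 participants.

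**The case against.** The strongest reply is that there is no conflict. The Arm 3 sentence in 10.3 says who is included; it does not say that others are excluded. Where the authors wanted an exclusive set, in 10.3.2, they wrote it as one. On this reading 10.3.1 supplies the first-dose rule and both sentences hold. But then the one-cycle condition would do no work for safety, and its placement directly after a one-dose rule for Arms 1 and 2 reads as a deliberate contrast. The reply shows that an analyst could reach the right set, not that the plan specifies it.

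Other points have partial force:

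- A cycle is defined by its 28 days, and 3.3.1 and 3.4.4 allow M7824 doses to be skipped or omitted. A participant who continues on two drugs is therefore not plainly excluded. This stands as a doubt about that subgroup, not about those who stop everything or die.
- Safety is a listed objective only for Arms 1 and 2, so a missing Arm 3 table is partly a matter of scope. However, 3.1.5 says that safety evaluation continues in Arm 3, and 10.3 defines a safety set for it.
- Arm 3 events do not go unseen. They are recorded from first intervention (6.1), can trigger the halting rules (3.2), and reach the DSMB (7.5.2) and the annual biosafety report (7.4.4). This stands, and it confines the problem to planned analysis and reporting.
- The counts are assumed. Also, 37 is the number evaluable for response, which additionally requires disease re-evaluation, so the 10.3 set could be somewhat larger. This stands.

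**Conclusion.** The point holds. The Arm 3 safety denominator is specified in two incompatible ways, and the arm-specific version is biased towards lower toxicity whenever early leavers have more toxicity than completers. The missing Arm 3 toxicity table is a separate, lesser gap that compounds it.

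The likely size is modest: about 4 points when two additional participants leave early and both have grade 3 or worse toxicity, over assumed base rates of 10.8% to 27.0%. For a toxicity confined to early leavers, the one-cycle set shows nothing. If most leave for progression or withdrawal, the difference is small or reverses. These figures rest on assumed event and leaver counts and on 37 standing for the one-cycle set.

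No Simon boundary, RP2D decision or safety oversight step depends on the choice. It should be corrected before the Arm 3 analysis, but it does not threaten the conduct of the trial.

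**What to change.** - In 10.3, define the Arm 3 safety set as all participants who receive at least one dose of any study drug, and align 10.3.1 and the last sentence of 10.4.5 with it.
- Keep the one-cycle condition for response evaluability only, where 10.3.2 already has it.
- In 10.4.5, extend the tabulation by grade and type of toxicity to Arm 3, separately for TNBC and HNSCC.

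The cost is a few sentences of wording and one table per cohort, from adverse event data already collected from first dose. No visits or participants are added, and both two-stage designs stay as they are.
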